**Outcome Measure**

**Primary outcome measures**

- Percentage of participants whose PLT reaches ≥

	
20*10^9/L without the need for PLT transfusion for consecutive 7 days during core study
 
Secondary outcome measures
 
 
• Percentage of participants whose PLT reaches ≥ 20*10^9/L without the need for PLT transfusion for consecutive 7 days during extended study;
 
• Percentage of participants without PLT response in the standard group but with PLT reconstruction after receiving avatrombopag;
 
• Percentage of participants with PLT ≥ 50*10^9/L without the need of PLT transfusion for consecutive 7 days during the core and extended study;
 
• The time to achieve PLT ≥ 20*10^9/L without the need of PLT transfusion for consecutive 7 days in both group;
 
• Proportion of participants achieving platelet reconstitution after 4 weeks of drug withdrawal;
 
• Volume of PLT transfusion;
 
• Hematopoietic reconstruction condition (absolute neutrophils, hemoglobin)
 
 
PLT reconstruction is defined as the status of PLT ≥ 20*10^9/L without the need of PLT transfusion for consecutive 7 days.

pSafety Measure
	
 
1. Liver and renal functions;
 
2. Occurrence and severity of transplantation-related complications;
 
3. Bleeding risk (WHO bleeding assessment scale);
 
4. Adverse events.
 

Study
	
Screening stage (Day 10~14 after Allo-HSCT)


process
	
 
1. Informed consent;
 
2. Subject's demographic information and basic information;
 
3. Medical history, current treatment, concomitant medication;
 
4. Vital signs, physical examination;
 
5. Transplantation mode and preprocessing scheme;
 
6. Blood test: blood routine, blood biochemical (including liver and renal functions), virus infection;
 
7. Pregnancy tests (women of childbearing age);
 
8. Eligibility criteria review.
 
 
Visit 1(Day 15 after Allo-HSCT, Initial treatment)
 
 
1. Blood test: blood routine, blood biochemical (including liver and renal functions);
 
2. Vital signs, physical examination;
 
3. Concomitant medication, including PLT transfusion;
 
4. Adverse events.
 
 
Visit 2-9 (one visit per 1~2 weeks. Visit 2, day 21±2; visit 3, day 28±2; visit 4, day 35±2; visit 5, day 42±2; visit 6, day 49±2; visit 7, day 56±2; visit 8, day 62±2; visit 9, day 70±2 after Allo-HSCT)
 
 
1. Blood test: blood routine, blood biochemical (including liver and renal functions);
 
2. Vital signs, physical examination;
 
3. Concomitant medication, including PLT transfusion;
 
4. Adverse events;
 
 
(Participants who achieved PLT reconstruction during the core and extended study period directly enter the follow up period;
 
Participants who do not respond to the standard

-----------------------	--------------------------------------------------------------------------------------------------------------------------------------------------------------------------------------------------------------------------------------------------------------------------------------------------------------------------------------------------------------------------------------------------------------------------------------------------------------------------------------------------------------------------------------------------------------------------------------------------------------------------------------------------------------------------------------------------------------------------------------------------------------------------------------------------------------------------------------------------------------------------------------------------------------------------------------------------------------------------------------------------------------------------------------------------------------------------------------------------------------------------------------------------------------------------------------------------------------------------------------------------------------------------------------------------------------------------------------------------------------------------------------------------------------------------------------------------------------------------------------------------------------------------------------------------------------------------------------------------------------

	
treatment can enter the extended study after visit 3 to receive avatrombopag treatment)
 
Visit 10 (day 28±5 after achieved PLT reconstruction)
 
 
1. Vital signs, physical examination;
 
2. Blood test: blood routine, blood biochemical (including liver and renal functions).
 
 
Long-term follow up is recommended.
 
Adverse events are closely observed and concomitant medication is recorded in detail during the study.


Concomitant Treatment
	
 
1. PLT transfusion is allowed according to the bleeding situation: PLT transfusion is given to participant when PLT account < 20*10^9/L, or between 21-60 *10^9/L with active bleeding;
 
2. G-CSF treatment (subcutaneous injection of G-CSF at 5 µg/kg/d from the first day after transplantation until the neutrophils count (ANC) recovered to ≥ 1*10^9/L);
 
3. Cyclosporine A, short courses of mycophenolate mofetil and methotrexate are allowed to use for the prevention of GVHD;
 
4. For medications that have been used before the trial, try to maintain the same dose during the trial;
 
5. Other TPO-RA (such as Eltrombopag and Romiplostim) should be prohibited during the study period;
 
6. Participants are allowed to take concomitant medications that are not specified as prohibited during the study period; Medications used one month prior to screening will be recorded on the case report form. All
 

	
prescription medicines, herbal medicines, nutritional supplements (including vitamins), and over-the-counter medicines should be recorded, as well as any changes in medication taken, including the dose. CYP2C9 or CYP3A4/5 medium or strong inducers may affect the exposure level of avatrombopag in vivo, and medication regimen should be comprehensively assessed by the investigator;
 
7. Observation of adverse events and concomitant medication assessment are conducted for all participants at each visit from the signing of informed consent to the end of the study;
 
8. All concomitant medications should be recorded and described in the corresponding section of the case report form (CRF).


Statistical Analysis
	
 
• The sponsor will utilize appropriately qualified individuals to supervise the conduct of the trial to make sure the data collection, entry and management are in accordance with good clinical practice (GCP);
 
• Corresponding database will be established and source data will be input independently;
 
• Data administrator uses Epidata software to compile data entry program and carry out following process. Two data administrators will independently enter and proofread the data in double copies to ensure the accuracy.
 
 
Sample size estimation
 
 
• 78 participants
 
 
Based on the known literature, 35% of patients in the control group and 60% of patient in the trial group were

estimated to achieve the primary endpoint. Under the condition of the number ratio of control to trial group 1:1,  $\alpha=0.05$  (bilateral) and  $1-\beta=0.9$ , the number of participants in the control group and the test group was 79 and 79 respectively, calculated by the pros and cons test method of the clinical controlled study with PASS software. Further taking into account a 20% shedding rate per group, 95 cases per group were actually needed, for a total of 190 cases

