**Withdrawal criteria**

1. PLT remains less than  $20 \times 10^9/L$  after two weeks' treatment of avatrombopag in a maximum dose of 60

	
mg/d (Solution: receive other treatment after withdrawal from the study);
 
 
2. The participant or his legal guardian requests a withdrawal ;
 
3. c poor compliance(medicine taken less than 80% of the prescribed amount or more than 120% of the prescribed amount);
 
4. With requirement of a medicine that is prohibited in the study;
 
5. With adverse events that discontinues the study;
 
6. With some unexplained serious complications;
 
7. Be pregnant during treatment;
 
8. Deemed unsuitable for further study by the investigator.
 
 
Trial Termination
 
 
1. Sponsor decides to stop the trial for safety reasons;
 
2. Independent ethics committee decides to stop the trial;
 
3. Principal investigator decides to stop the trial.
 

Investigational Product
	
 
• Name: avatrombopag;
 
• Dosage form: tablet;
 
• Specification: 20 mg/tablet.
 

Treatment Design
	
 
• The whole study is divided into two stages, including 4-weeks' core study and 4-weeks' extended study;
 
• During the core study, participants are randomly assigned into the avatrombopag group and the rhTPO treatment group(standard group) with 1:1 ratio. The initial dose of avatrombopag is 20 mg/d. If the patient's PLT count remains less than <math>20 \times 10^9/L</math> after one week, the maximum dose was increased to 40 mg/d.
 
 
Avatrombopag will be taken orally with food. The rhTPO

will be subcutaneously injected with dosage of 300 U/kg/d;

- After the end of the core study, participants in the avatrombopag group who does not meet the withdrawal indication can be enrolled in the extended study and continue the avatrombopag treatment with a maximum dose of 60 mg/d. Participants who does not respond to treatment in the rhTPO group (PLT < 20\*10^9/L ) can also be enrolled in the extended study to receive avatrombopag treatment, by titrating avatrombopag in the dose of 20-60 mg/d according to the participants' condition;

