#### **Statistical analysis method**

- PLT and other mean variation trends were processed by repeated measurement data analysis of variance; Kaplan-Meier survival analysis was used to estimate the recovery of PLT count, cumulative predicted survival rate, cumulative recurrence rate of malignant hematologic disease, cumulative mortality associated with transplantation, and cumulative incidence of GVHD, and log-rank test was performed. Independent sample nonparametric test was used to analyze the accumulative demand of PLT suspension. The statistical process and graph were all run on SPSS 13.0 software. All tests were bilateral, and  $P \leq 0.05$  was considered to be significant. The PLT recovery time, granulocyte implantation time and PLT infusion number were compared by one-way analysis of variance. OS and DFS are estimated by Kaplan-Meier method. Risk factor analysis: variables: age, sex, HLA match, CD34+ cell number, incidence of GVHD within 100 days after transplantation, CMV infection rate. Multivariate Cox regression analysis was performed on the factors with significant differences ( $P < 0.05$ ) by one-way analysis of variance.

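### PLT ≥50 is measured across the switch to avatrombopag, and time to PLT ≥20 and transfusion volume have no window, so these secondary comparisons may set avatrombopag against rhTPO-then-avatrombopag

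*Combined protocol and SAP*

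**What the plan says.** All references are to the combined protocol and SAP.

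- **Outcome Measure.** The primary outcome (PLT ≥20 for 7 days without transfusion) is limited to the core study. Among the secondary outcomes, the PLT ≥50 percentage is counted "without the need of PLT transfusion for consecutive 7 days during the core and extended study". Time to PLT ≥20 is defined "without the need of PLT transfusion for consecutive 7 days in both group", with no end date. Volume of PLT transfusion is listed with no period at all. Two other secondary outcomes do keep the stages apart: the PLT ≥20 percentage during the extended study, and reconstruction on avatrombopag among standard-group non-responders.
- **Treatment Design.** After the 4-week core study, rhTPO participants with PLT <20 "can also be enrolled in the extended study to receive avatrombopag treatment, by titrating avatrombopag".
- **Study process.** Treatment starts on day 15 after transplant. Non-responders to the standard treatment may enter the extended study after visit 3, which is day 28±2. Participants who reach reconstruction leave the visit schedule for follow-up.
- **Statistical analysis method.** Platelet recovery is analysed by Kaplan-Meier and log-rank, and recovery time and infusion number by one-way analysis of variance. For transfusion, "Independent sample nonparametric test was used to analyze the accumulative demand of PLT suspension". No window, no handling of the switch and no estimand is stated for any of these. No test is named for the percentage outcomes.

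**The concern.** The switch goes one way and is part of the design. If extended-study data enter a comparison by arm, a participant who fails rhTPO and then recovers on avatrombopag counts as a success, and contributes a recovery time, in the rhTPO arm. Any transfusions avoided after the switch are also credited to rhTPO.

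The synopsis names promoting reconstruction and reducing platelet transfusion as objectives, and transfusion volume is the only listed outcome that measures the amount transfused. A diluted difference here could be read as the drugs being similar when it partly reflects both arms having received the same drug.

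Transfusion volume has a second difficulty. Without a fixed window, the length of observation depends on the participant's course. Someone withdrawn early may appear to have needed little.

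**Working it through.** **Inputs.** Sample size estimation gives "35% of patients in the control group and 60% of patient in the trial group" for the primary endpoint, 1:1 allocation, two-sided α = 0.05 and power 0.90. It states 79 per arm before dropout, and the synopsis also gives a total of 78 (39 per arm). Both sizes are used below; the conflict between them is a separate matter.

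**1. The plan's own figure.** Unpooled two-proportion formula:
n = (1.960 + 1.282)² × (0.35 × 0.65 + 0.60 × 0.40) / 0.25² = 78.6, so 79 per arm. Reproduced.

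**2. How many could switch.** At a 35% core response, up to 65% of the rhTPO arm misses the endpoint: 0.65 × 39 = 25.4, or 0.65 × 79 = 51.4. This is an upper approximation, because missing the 7-day endpoint is not the same as PLT <20.

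**3. Cumulative PLT ≥20 by the end of the extended study.** Assume a share q of core non-responders in each arm responds on avatrombopag in the second stage.
- rhTPO arm: 0.35 + 0.65q. Avatrombopag arm: 0.60 + 0.40q. Difference: 0.25 × (1 − q).

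| q | rhTPO arm | avatrombopag arm | gap (points) | power, 79/arm | power, 39/arm |
|---|---|---|---|---|---|
| 0 (core only) | 35% | 60% | 25 | 0.89 | 0.60 |
| 0.2 | 48% | 68% | 20 | 0.73 | 0.43 |
| 0.4 | 61% | 76% | 15 | 0.53 | 0.29 |
| 0.6 | 74% | 84% | 10 | 0.34 | 0.19 |

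Power here is for a two-sided test of two proportions, used as an illustration. If q differs by arm, say 0.4 in rhTPO switchers and 0.2 in avatrombopag continuers, the result is 61% against 68%, a gap of 7 points.

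**4. Time to PLT ≥20, log-rank test by simulation.** Constant hazards are taken from 35% and 60% over 28 days: hazard ratio ln(0.40)/ln(0.65) = 2.13. The switch is at day 28 and follow-up ends at day 56. Avatrombopag participants keep their own hazard, except in the q = 0.2 row.

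| Scenario | 39/arm | 79/arm |
|---|---|---|
| Core only, 28 days | 0.62 | 0.90 |
| 56 days, all switch and recover at the avatrombopag rate | 0.43 | 0.71 |
| 56 days, all switch, q = 0.2 in both arms | 0.54 | 0.82 |
| 56 days, half switch and recover at the avatrombopag rate | 0.65 | 0.89 |
| 56 days, all switch but recover only at the rhTPO rate | 0.79 | 0.98 |

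Differences of a few hundredths are within simulation error. The half-switch row shows no material loss, and the last row shows a gain.

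**5. When the switch occurs.** Treatment Design puts it after 4 weeks of treatment, about day 15 + 28 = 43 after transplant. Study process allows it after visit 3, about 28 − 15 = 13 days into treatment. On the second reading, rhTPO participants could receive avatrombopag inside the 4-week core window.

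**What cannot be computed.** The 35% and 60% are for PLT ≥20. The documents give no rates for PLT ≥50 and no transfusion volumes, so those two outcomes cannot be sized.

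**The case against.** The strongest reply is that the plan already separates the stages where it matters most. The primary outcome is core only, one secondary outcome is confined to the extended study, and another isolates the rhTPO non-responders treated with avatrombopag. All of this is true, and a reader who inferred that nothing in the plan separates the periods would be wrong. It does not settle the three outcomes at issue.

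It is also tempting to read all three as stated 8-week comparisons. Only PLT ≥50 is written that way, and its wording could mean that each stage is reported separately; no between-arm test of it is specified. For the other two the defect is a missing window, which permits contamination without prescribing it.

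A reader might further infer that 8-week results are invalid, or that a null result would be uninterpretable. The documents do not support that. By assigned arm, such results remain a valid randomised comparison of starting avatrombopag with starting rhTPO and moving to avatrombopag on failure, and recoveries reached before a switch are unaffected. But the plan never declares that this is the question.

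Nor does adding the second 4 weeks necessarily lose power. The large loss needs every non-responder to switch and recover at the full avatrombopag rate. Treatment Design makes the switch optional and limits it to PLT <20.

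**Conclusion.** The concern holds as one of unspecified windows and unspecified switch handling. PLT ≥50 is stated over both stages; time to PLT ≥20 and transfusion volume are open-ended. As written, the plan allows recoveries on avatrombopag to be credited to the rhTPO arm, so a result presented as drug against drug may be a comparison of strategies.

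For PLT ≥20, the dilution is from 25 points to 20, 15 or 10 for an assumed common q of 0.2, 0.4 or 0.6. The effect on log-rank power depends on how many switch and how they respond. Where avatrombopag works after rhTPO failure as well as it does first-line, it ranges from no material loss (half switch) to a fall of 0.19 at either sample size (all switch). These figures rest on assumed post-failure rates and, for the log-rank test, on constant hazards.

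The primary outcome has its own window and is outside this point, with one reservation: if the switch can occur after visit 3, core data, including the primary outcome, could contain avatrombopag exposure in the rhTPO arm.

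**What to change.** 1. Define the between-arm comparisons of these three outcomes on the randomised 4-week core window, by assigned arm:
   - PLT ≥50 for 7 days by the end of core.
   - Time to PLT ≥20 with administrative censoring at the end of core.
   - Transfusion volume as a total over the fixed core window, including days after response. A rate per day observed should be avoided, because responders leave the schedule early. For illustration, 4 units in 10 days before recovery is 0.40 per day, while a non-responder with 8 units in 28 days is 0.29 per day, so the responder would look worse.
2. Report extended-study results descriptively by treatment sequence (avatrombopag throughout; rhTPO then avatrombopag). Label any 8-week between-arm result as a comparison of strategies.
3. Reconcile Treatment Design and Study process on when the switch may occur. If it can fall within core, prespecify its handling. Simple censoring at the switch should not be used: the switch is triggered by low platelets, so that censoring would be informative.

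**Cost.** The change is mainly to outcome and analysis wording. Concomitant medication is already to be recorded to the end of the study, but it should be confirmed that platelet counts and transfusions after reconstruction are captured to the end of core, since responders move to a follow-up with a single count. The price is fewer events in the secondary between-arm tests, and late PLT ≥50 responses move to a descriptive table.

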- Patients who achieved PLT reconstruction during the core study and the extended study period are followed up to 4 weeks after investigational product withdrawal, and PLT count is measured for one time during the follow up;
- Adjustment Indication: When PLT ≥ 50\*10^9/L excluding the factor of blood transfusion, the dosage of avatrombopag and rhTPO will be eventually decreased and stopped according to clinicians.

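### Visit 10 is timed from platelet reconstruction although its outcome is defined from drug withdrawal, and reconstructed participants leave the count schedule before the ≥50×10⁹/L outcome can be shown

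*Combined protocol and SAP*

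**What the plan says.** All references are to the protocol synopsis in the combined protocol and SAP. Reconstruction is defined under Outcome Measure as a platelet count of at least 20×10⁹/L for 7 consecutive days without transfusion.

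**Leaving the schedule.** Study process (Visits 2–9): "Participants who achieved PLT reconstruction during the core and extended study period directly enter the follow up period". No condition is set on the drug having been stopped, and the rule covers both arms. Treatment Design says that reconstructed participants "are followed up to 4 weeks after investigational product withdrawal, and PLT count is measured for one time during the follow up".

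**Stopping the drug.** Treatment Design, Adjustment Indication: once the count is ≥50×10⁹/L, apart from any effect of transfusion, "the dosage of avatrombopag and rhTPO will be eventually decreased and stopped according to clinicians".

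**Entering the extended study.** Treatment Design says that "participants in the avatrombopag group who does not meet the withdrawal indication can be enrolled in the extended study". For the other arm it names only "Participants who does not respond to treatment in the rhTPO group", meaning a count below 20×10⁹/L, and these participants then receive avatrombopag.

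**Outcomes.** The secondary outcomes include the percentage with ≥50×10⁹/L "without the need of PLT transfusion for consecutive 7 days during the core and extended study", and the "Proportion of participants achieving platelet reconstitution after 4 weeks of drug withdrawal".

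**Off-drug visit.** Study process: "Visit 10 (day 28±5 after achieved PLT reconstruction".

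**The concern.** **(a) Two time origins for one outcome.** The off-drug outcome asks whether platelets hold 4 weeks after treatment ends. The only visit that can supply it is timed from reconstruction. Stopping is tied to ≥50×10⁹/L and reconstruction to ≥20×10⁹/L, so treatment may continue after reconstruction. Visit 10 then falls too early, or even on drug, and the reported proportion would not be the one listed.

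**(b) An outcome that outlasts its measurement.** A participant who reconstructs at ≥20×10⁹/L leaves for a phase with one planned count. One count cannot show a 7-day run at ≥50×10⁹/L. Those affected are responders, the group this outcome is meant to describe.

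Observation may also differ by arm. Treatment Design permits avatrombopag responders to continue in the extended study but names only non-responders for rhTPO, whereas Study process moves reconstructed participants in both arms out.

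**Working it through.** **Inputs from the documents.** Treatment starts on day 15. Visits 2–9 fall on days 21, 28, 35, 42, 49, 56, 62 and 70 (each ±2), so nominal gaps from visit 1 are 6, 7, 7, 7, 7, 7, 6 and 8 days. Visit 10 is 28±5 days after reconstruction. The plan gives no figure of its own to reproduce here. The time from reconstruction to last dose and the rate of platelet rise are not given, so both are assumptions below.

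**(a) Visit 10 against drug withdrawal.** Let reconstruction be day R and the last dose day R+t. Visit 10 is on day R+28 (±5), so days off drug = 28−t, with a range of 23−t to 33−t.

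| t (assumed, days) | Days off drug at Visit 10 |
|---|---|
| 0 | 28 (23 to 33) |
| 5 | 23 (18 to 28) |
| 7 | 21 (16 to 26) |
| 14 | 14 (9 to 19) |
| 21 | 7 (2 to 12) |
| 28 | 0 (5 days before to 5 days after the last dose) |

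Four weeks off drug needs 33−t ≥ 28, that is t ≤ 5, and at t = 5 only on the last day of the window. The target day matches only at t = 0.

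As an illustration, suppose a linear rise of r×10⁹/L per day and a last dose on the day 50×10⁹/L is reached. Then t = 30/r − 7, counted from the seventh day at ≥20×10⁹/L. For r = 2.5, 2, 1.5 and 1, t is 5, 8, 13 and 23 days. Gradual dose reduction after 50×10⁹/L would make t larger.

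**(b) Scheduled counts lost at exit.** Remaining scheduled counts = 9 − exit visit number.

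| Exit visit | 3 | 4 | 5 | 6 | 7 | 8 | 9 |
|---|---|---|---|---|---|---|---|
| Counts lost | 6 | 5 | 4 | 3 | 2 | 1 | 0 |

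Exit at visit 2 would lose 7, but it requires a count already ≥20×10⁹/L at visit 1. In practice the range is about 0–6.

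**What scheduled counts can still show.** Before exit they can document the ≥50×10⁹/L run only if the counts that establish reconstruction are themselves already at that level. With counts exactly 7 days apart, a linear rise, and the crossing of 20×10⁹/L uniform within a gap, the documented share is 1 − 30/(7r). The table sets this beside a simulation with ±2-day windows, crossing uniform over days 15–43. The lower simulated figure accepts any two consecutive counts as 7 days; the upper one requires counts at least 7 days apart.

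| r (assumed) | Formula | Simulated, ±2 days |
|---|---|---|
| 5 | 14% | about 20–42% |
| 8 | 46% | about 48–64% |
| 15 | 71% | about 72–82% |

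The formula gives zero below r = 30/7 ≈ 4.3; the simulation with windows does not. No simulated participant left at visit 2. These shares are illustrative: they move with an assumed rate and with how 7 days is scored.

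**By arm.** If responders in both arms leave, as Study process says, both arms lose counts. If avatrombopag responders continue, as Treatment Design permits, and rhTPO responders leave, only the rhTPO arm loses them. The first reading tends to shrink a true difference and the second to inflate the avatrombopag advantage. The documents do not say which applies.

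**The case against.** **Unscheduled counts.** The strongest objection is that the primary outcome also needs 7 consecutive days, while scheduled visits are 6–8 days apart. If routine counts between visits support the primary outcome, they may also support the ≥50×10⁹/L outcome. This stands in part: the documents do not exclude such counts. But they do not plan their collection after exit either. The exit rule takes away later scheduled counts and leaves those before exit.

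**Follow-up may start at withdrawal.** Treatment Design can be read this way, and its adjustment rule cannot be applied to someone still on drug without further counts. On that reading the loss in (b) is smaller. Study process, however, makes the move at reconstruction, so the two sections still need reconciling.

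**Permissive wording.** The extended-study rule for avatrombopag allows continuation and does not require it. This weakens the contrast between arms without removing it, since sites could follow the text and still observe responders differently.

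**A stronger reading.** A reader might infer that the ≥50×10⁹/L comparison is biased by a known number of percentage points, or in favour of a known arm. The documents do not support this. The size rests on an unstated share of responders who reach the level only after exit, and the direction reverses with the reading. After the core study, rhTPO non-responders receive avatrombopag, so the arms are no longer cleanly separated whatever the exit rule. The statistical methods section also names no between-arm test specifically for this outcome.

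None of these objections touches (a), where the two time origins differ on the face of the text.

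**Conclusion.** The concern holds in two parts.

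(a) is firm and needs no model. As timed, Visit 10 cannot be 4 weeks off drug if the last dose is more than 5 days after reconstruction, and nothing in the plan requires the drug to stop within that time. How many participants this affects is not determinable from the documents.

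(b) is a real gap of unknown size. A participant who sustains ≥50×10⁹/L only after leaving the schedule has no planned counts to show it. The number depends on the rate of rise, on use of unscheduled counts, and on whether follow-up begins at reconstruction or at withdrawal. Observation may differ by arm, but neither direction nor size is established.

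It would go too far to conclude that the primary outcome is compromised by the exit rule: that rule does not remove the counts before exit on which it is scored. The effect is on two secondary outcomes.

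**What to change.** 1. Time the off-drug assessment from the recorded last dose, so that it measures the listed outcome. State how the 7-day, transfusion-free definition is to be met with a single count. Platelet transfusions at that visit should be recorded, as Concomitant Treatment item 7 already implies.
2. Keep platelet counts and transfusion records on the existing visit 2–9 calendar for every randomised participant in both arms, reconstructed or not. Alternatively, retrieve routine counts for those dates.
3. Reconcile Treatment Design and Study process on who leaves the schedule, when follow-up starts and when Visit 10 falls, with the same observation rule in both arms.

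Cost: a minor amendment. Item 2 means in practice about 0–6 further routine counts per responder, or retrieval of counts already taken. The Visit 10 anchor and item 3 are wording changes. If item 2 cannot be done by either route, the ≥50×10⁹/L outcome should not be compared between arms. The primary outcome stays as it is. This concerns observation and timing of assessment only; no dose or stopping rule is proposed.

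### The visit schedule lets rhTPO non-responders switch to avatrombopag after visit 3, about 13 days into the 28-day core study on which the primary outcome is measured

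*Combined protocol and SAP*

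**What the plan says.** All references are to the synopsis, which is the whole of the combined protocol and SAP.

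- **Treatment Design.** "The whole study is divided into two stages": a core study of 4 weeks and an extension of 4 weeks. The bullet on the extension opens with "After the end of the core study, participants in the avatrombopag group". Its next sentence, beginning "Participants who does not respond to treatment in the rhTPO group", says that controls with PLT below 20 may also join the extension and receive avatrombopag.
- **Study process.** Treatment begins at "Visit 1(Day 15 after Allo-HSCT, Initial treatment". The later visits include "visit 3, day 28±2; visit 4, day 35±2; visit 5, day 42±2" and end with "visit 9, day 70±2 after Allo-HSCT". A note under visits 2-9 says that patients not responding to standard treatment "treatment can enter the extended study after visit 3 to receive avatrombopag treatment".
- **Outcome Measure.** The primary outcome is the percentage reaching the PLT threshold "without the need for PLT transfusion for consecutive 7 days during core study". Response in the extension, and reconstruction in controls after they receive avatrombopag, are separate secondary outcomes.
- **Statistical analysis data set.** The main efficacy population is the FAS, described as following the ITT principle. Treatment that seriously interferes with efficacy evaluation is listed among the grounds for leaving the PPS.

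No section says how a control who starts avatrombopag before the end of the core study is scored for the primary outcome.

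**The concern.** The two sections put entry to the extension about two weeks apart, and nothing reconciles them. One site could switch a control at visit 3 while another keeps a similar control on rhTPO to visit 5, both within the plan.

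The early switch is open to one arm only. An avatrombopag patient without response stays on avatrombopag, with dose escalation. The lack-of-response withdrawal rule for that arm refers to two weeks at up to 60 mg/d, a dose that Treatment Design gives only in the extension. A control who switches at visit 3 has no rhTPO outcome for the rest of the core study. The primary percentage for the control arm then depends on how many patients switch and how they are scored.

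**Working it through.** **1. Day arithmetic (inputs from Treatment Design and Study process)**

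- Core study: 28 treatment days starting on day 15, so the last is day 15 + 27 = 42. This is visit 5 (day 42±2).
- Check on the visit grid: visit 9 − visit 5 = 70 − 42 = 28 days, which fits a 4-week extension after visit 5.
- Time on treatment at visit 3: 28 − 15 = 13 days (26 − 15 = 11 to 30 − 15 = 15).
- Share of the core study elapsed: 13/28 = 46% (11/28 = 39% to 15/28 = 54%).

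**2. The plan's own design figure (Sample size estimation)**

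With 35% against 60%, two-sided 0.05 and 90% power, using unpooled variance:

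n = [0.35×0.65 + 0.60×0.40] × (1.960 + 1.282)² / 0.25² = 79 per group, as stated.

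The illustrations use 79 per arm and also 39 per arm (78/2), because the plan gives both 78 participants and 79 per group.

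**3. Illustration A: control follow-up ends at the switch**

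Assumptions, none of them in the documents: constant hazard of starting a 7-day run; only controls with PLT below 20 switch, so a run already under way is kept; responses after the switch are not counted; uncorrected chi-square test at two-sided 0.05.

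- A run must start by treatment day 21 to finish by day 28. To give 35% by day 28, h = −ln(0.65)/21 = 0.0205 per day.
- Control responses kept if all eligible patients switch on treatment day s: 1 − exp(−h·s) = 0.202 (s = 11), 0.234 (s = 13), 0.265 (s = 15).
- Scored control rate if a fraction f of the later responses is lost: 0.35 − f × (0.35 − kept).

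Chance of declaring avatrombopag superior when the true rate is 35% in both arms (exact binomial enumeration, s = 13):

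| Later control responses lost | Scored control rate | 39 per arm | 79 per arm |
|---|---|---|---|
| none | 35% | 2.6% | 2.6% |
| a quarter | 32% | 5% | 6% |
| half | 29% | 8% | 12% |
| all | 23% | 21% | 36% |

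Across the visit 3 window (s = 15 to 11), the ranges are 6-11% at 39 per arm and 8-17% at 79 with half lost, and 13-32% and 21-56% with all lost.

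**4. Illustration B: response counted to day 42 in the randomised arm**

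Same model, true rates 35% and 60%. After the switch a control takes the avatrombopag hazard, ha = −ln(0.40)/21 = 0.0436 per day, for the remaining 21 − 13 = 8 days of the start window.

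- All switch: 0.234 + 0.766 × [1 − exp(−8 × 0.0436)] = 0.460. Difference 60 − 46 = 14 points.
- Half switch: (0.350 + 0.460)/2 = 0.405. Difference 60 − 40.5 = about 20 points.
- Power at 79 per arm (same exact test) falls from 88% to 68% (half switch) or 41% (all switch).

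**The case against.** **The conflict is partly inferred.** The phrase on the end of the core study grammatically governs the avatrombopag group; the sentence on rhTPO non-responders gives no time of its own. The visit note is permissive, and entry after visit 5 satisfies both sections. It may be a slip, an earliest bound, or intended. All this is fair. But the extension is by construction the stage after a 4-week core study, and even an earliest bound at visit 3 permits a switch about two weeks before that core study ends.

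**A reader might infer that the plan is biased towards avatrombopag.** The documents do not support that. Listing post-switch reconstruction as a secondary outcome suggests that such responses are kept out of the primary one. Against that, the ITT language for the FAS leans towards counting the randomised arm's outcome through the whole window, and then the bias is conservative. Neither scoring is stated.

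**A reader might also infer that controls lose half of their chance to respond.** That overstates it. On the model above, a run must start by day 21, so 13/21 = 62% of the start window and 23.4/35 = 67% of control responses survive even if every eligible control switches.

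**The existing analyses offer some protection.** An early switch may count as a serious violation for the PPS, and disagreement between PPS and FAS must be examined. Statistical analysis method also specifies Kaplan-Meier and log-rank for PLT recovery. In a simulation of 10,000 runs under the same constant hazard, with switchers censored at day 13 and response dated to the start of the run, false superiority stayed at 2.2-2.6%. This is partial mitigation. PPS violations are defined only at data review, the log-rank result depends on how response is dated, and neither settles the primary percentage.

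**Conclusion.** The point holds. The visit note and Treatment Design give different times for control entry to the extension, and the visit note, followed as written, allows a control-only switch to the experimental drug at treatment day 11-15 of 28. If sites follow Treatment Design, the primary outcome is unaffected.

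That conclusion needs only the day arithmetic. The size and direction of any bias are not established. They depend on the scoring rule, the fraction of controls who switch and the timing of responses, none of which the plan gives. The two illustrations show that either scoring can distort the comparison materially, in opposite directions. They are not estimates of what will happen, and their extremes require every eligible control to switch despite Treatment Design.

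This should be corrected before enrolment, because rhTPO outcomes that were never observed cannot be restored to the primary percentage without further assumptions.

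**What to change.** 1. **Study process, note under visits 2-9:** replace entry after visit 3 with entry after visit 5 and not before 28 days of rhTPO are complete (day 42). The second condition is needed because visit 5, at day 42±2, can fall on day 40.
2. **Outcome Measure:** define the primary window as first dose to day 42 in both arms, with the 7-day run completed inside it.
3. **Scoring:** for any control who still starts avatrombopag early, name one rule in advance and report the primary result under both: (a) response counted to day 42 in the randomised arm; (b) non-responder unless the 7-day run was completed before the switch. Rule (b) alone would build in a penalty on the control arm, and rule (a) alone would credit rhTPO with responses on avatrombopag, so both are needed.

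If the sponsor does intend the switch at visit 3, Treatment Design and the primary window must be changed to match.

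**Cost:** a changed visit condition and a few sentences, with no extra patients or visits. Compared with the visit note, control non-responders wait about two more weeks for avatrombopag. Treatment Design already implies that wait, and PLT transfusion remains available under Concomitant Treatment.
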